### Exploratory Endpoints

For the exploratory outcomes measured at baseline and week 12, when normality assumption holds, we will test the association between outcomes and the arms of the study using linear mixed model; otherwise generalized linear mixed effects models will be used with the appropriate distribution function. Random study site effect will be tested; if significant, it will be included in the modeling; if insignificant, the models will be simplified to linear or generalized linear models. Appropriate transformations may be used to satisfy the normality assumptions of the model, if needed. Baseline corticosteroid/immunosuppressive therapy use will be included as a covariate in the models.

Some exploratory outcomes may include measures during or at the end of OLE. For participants that continue into the open label phase of the study, we will evaluate change for two time ranges. We will examine the overall change across the study (baseline to OLE/EOT (Week 36)). Then, we will examine change during the open label phase (DBP/EOT (Week 12) to OLE/EOT (Week 36)). When evaluating these changes, analyses will be stratified by treatment status during the blinded phase of the study. Changes of the OLE endpoints will be tested against 0 using paired t tests or signed rank tests when lacking of normality. Mean change and two-sided 95% confidence intervals will be presented.

### Safety outcomes

Adverse events will be summarized for each treatment group in the intent-to-treat population. The number and percentage with exact 95% confidence intervals of participants experiencing each adverse event category and the number of adverse events that occurred will be presented. Serious adverse events will be summarized using the same approach.

The following descriptive data displays and summaries will be provided for vital sign, urinalysis, blood chemistry and hematology measures. For continuous measures, scatter plots of each measure for each treatment group will be presented with the baseline measure on the x-axis and the week 12 measure on the y-axis. A 45-degree reference line will be included in each plot. For categorical measures, two-way frequency tables will be provided for each treatment group that include baseline result versus week 12 result. Abnormal (clinically significant) results will be reported. Any clinically relevant changes in physical exam data will be described for each treatment group.

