13.5.5. Safety outcomes

Adverse events will be summarized for each treatment group. The number and percentage of participants experiencing each adverse event category and the number of adverse events that occurred will be presented. Relative risk and exact 95% confidence intervals will be reported for each treatment group and each adverse event category. Serious adverse events will be summarized using the same approach. The following descriptive data displays and summaries will be provided for vital sign, urinalysis, blood chemistry and hematology measures. For continuous measures, scatter plots of each measure for each treatment group will be presented with the baseline measure on the x-axis and the week 12 measure on the y-axis. A 45-degree reference line will be included in each plot. For categorical measures, two-way frequency tables will be provided for each treatment group that include baseline result versus week 12 result. Any clinically relevant changes in physical exam data will be described for each treatment group.

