## Introduction

The primary objective of this study is to assess the efficacy and safety of Dupilumab in the treatment of Eosinophilic Gastritis. This document outlines the statistical methods to be implemented during the analyses of data collected within the scope of Consortium of Eosinophilic Gastrointestinal Disease Researchers' Protocol CEIGR 7810 titled "A Randomized, double-blind, placebo-controlled clinical trial to evaluate the efficacy of dupilumab (anti-IL4ra) in subjects with eosinophilic gastritis". This Statistical Analysis Plan (SAP) was prepared in accordance with CEGIR 7810 protocol, V6.0, dated 12/6/2023.

The purpose of this Statistical Analysis Plan (SAP) is to provide a framework in which answers to the protocol objectives may be achieved in a statistically rigorous fashion, without bias or analytical deficiencies, following methods identified prior to database lock. Specifically, this plan has the following purposes:

- To prospectively outline the specific types of analyses and presentations of data that will form the basis for conclusions.
- To explain in detail how the data will be handled and analyzed, adhering to commonly accepted standards and practices of biostatistical analysis. Any deviations from these guidelines must be substantiated by sound statistical reasoning and documented in writing in the final clinical study report (CSR) or manuscript.

The analyses described in this analysis plan are consistent with the analyses described in the study protocol. The order may be changed for clarity. If there are discrepancies between the protocol and SAP, the SAP will serve as the definitive analysis plan.

Any analysis performed not prospectively defined in this document will be labeled as post hoc & exploratory.

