## Overview and Objectives of Study Design

**Overview:** This is a phase 2, multi-center, randomized, double-blind, placebo-controlled trial testing the efficacy of dupilumab vs. placebo in eosinophilic gastritis (EoG) with or without concurrent esophageal and/or duodenal eosinophilia. Potential participants will be screened during an 8-week screening period. An esophagogastroduodenoscopy (EGD) with biopsies will be performed to determine study eligibility, and participants will be enrolled based on the presence of active disease and their ability to meet the study inclusion and exclusion criteria. Qualifying participants will be blindly randomized 1:1 to either study drug(dupilumab) or placebo and will receive 600 mg once followed by 300 mg doses every two weeks of study treatment (for a total of 6 injections). During the treatment period, participants will be monitored for adverse events/reactions and will complete patient reported outcome metrics to track their symptoms and general wellbeing. At the end of the 12-week randomized treatment period (EOT), a repeat endoscopy with biopsies will be performed to assess the change in gastric eosinophil count from pre-to-post treatment. Participants and site study staff will remain blinded to the endoscopy biopsy results until all participants have completed the DBP EOT visit. Study participants who complete the 12-week treatment phase (whether on drug or placebo) will have the option to continue into an open-label extension (OLE) and laboratory studies and patient reported outcomes will be completed as indicated in the schedule of activities (SOA). The OLE ensures that every participant gets access to the drug and will provide data on the effect of a longer treatment period in comparison to the initial 12 weeks in the double-blind phase. A final study EGD will be performed two weeks after the last dose of the study drug. All participants will be followed for an additional 12 weeks after the last dose of study drug regardless of whether they participate in the OLE.

**Objectives:** The central hypothesis of this study is that dupilumab is safe and efficacious for reducing eosinophilia and a Th2 gene profile in EoG.

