### **Statistical Analysis Changes From the Protocol**

Changed the analysis population for the key primary and secondary efficacy outcomes to the complete case ITT. The rationale was that a single participant in the placebo arm dropped out before the end of the double blind. The initial SAP stated that multiple imputation would be used if missing data occurred. However, multiple imputation considers a multitude of plausible values and accounts for this uncertainty in the modelling. While it is a statistically robust approach, graphing the observed data points would exclude the missing data thus providing a mismatch between the graphical data and the statistical models used. Further, there was striking agreement between the results using the imputed and complete case datasets.

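### The SAP replaces the protocol's relative risk for adverse events with separate per-arm percentages, leaving no planned between-arm safety estimate, and does not declare the change

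*SAP*

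**What the plan says.** Protocol section 13.5.5 starts with counts and percentages per arm, then adds: "Relative risk and exact 95% confidence intervals will be reported for each treatment group and each adverse event category". Serious events are handled the same way.

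The SAP section Safety outcomes follows that text closely but has no relative risk. It says "Adverse events will be summarized for each treatment group in the intent-to-treat population", and the interval is now attached to each arm's own percentage: "The number and percentage with exact 95% confidence intervals of participants experiencing each adverse event category". Serious events again follow the same approach. The SAP's Safety objectives, Safety Endpoints and General Principles supply no between-arm safety estimate either.

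On how the two documents relate, the SAP Introduction states "The analyses described in this analysis plan are consistent with the analyses described in the study protocol" and also "If there are discrepancies between the protocol and SAP, the SAP will serve as the definitive analysis plan". It labels any analysis it does not define in advance as post hoc and exploratory. The section Statistical Analysis Changes From the Protocol has one entry, which concerns efficacy: "Changed the analysis population for the key primary and secondary efficacy outcomes to the complete case ITT". The SAP Revision History does not mention a safety change.

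Safety is part of what the trial sets out to address: "The central hypothesis of this study is that dupilumab is safe and efficacious" (SAP, Overview and Objectives of Study Design).

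**The concern.** A contrast specified in the protocol has disappeared from the governing document without being declared. Because the SAP prevails and treats anything it does not define as post hoc, a relative risk that the protocol promised in advance would have to be reported as post hoc if someone added it later.

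The double-blind phase is the only part of this trial with a placebo comparison; everyone in the open-label extension receives dupilumab. If the hypothesis includes safety, this is where drug and placebo can be set against each other. A percentage with its own interval describes each arm. It gives neither the size of the difference nor how uncertain that difference is. A reader given only two overlapping intervals may conclude that the arms are alike when a direct contrast would say otherwise.

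**Working it through.** **Comparing the texts.** Per adverse event category:

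| | Protocol 13.5.5 | SAP Safety outcomes |
|---|---|---|
| Count and percentage per arm | yes | yes |
| Exact 95% interval | listed with the relative risk | on each arm's percentage |
| Between-arm estimate | relative risk | none |
| Listed as a change | – | no |

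The protocol's wording is loose, since a relative risk cannot be reported for one treatment group. It needs two groups, so the workable reading is dupilumab versus placebo within each category.

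**Inputs.** Neither document gives a power or precision figure for safety, so there is none to reproduce. The arm size is 20, from 40 participants randomised 1:1 (protocol 3.6) and the sample size section. The documents give no adverse event rates for this trial, so the event counts below are assumptions.

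**Per-arm intervals (the SAP display).** Clopper-Pearson for x of n: the lower limit is the 2.5% quantile of Beta(x, n−x+1), and the upper limit is the 97.5% quantile of Beta(x+1, n−x). With n = 20:
- x = 8: 40%, interval 19.1 to 63.9%
- x = 1: 5%, interval 0.1 to 24.9%

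These overlap between 19.1% and 24.9%.

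**Direct contrast for the same counts.**
- Fisher's exact test, 9 events in 40 people: p = 2 × [C(20,8)·C(20,1) + C(20,9)] / C(40,9) = 2 × (2,519,400 + 167,960) / 273,438,880 = 0.020.
- Risk difference: 40 − 5 = 35 percentage points.
- Relative risk: (8/20)/(1/20) = 8.0. The exact unconditional score interval (two one-sided 2.5% tests) is about 1.3 to 213. The log approximation, exp[ln 8 ± 1.96·√(1/8 − 1/20 + 1/1 − 1/20)], gives 1.1 to 58.

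**Other splits.**

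| Events | Per-arm exact 95% intervals | Fisher p |
|---|---|---|
| 9/20 vs 2/20 | 23.1–68.5% and 1.2–31.7% (overlap) | 0.031 |
| 5/20 vs 0/20 | 8.7–49.1% and 0–16.8% (overlap) | 0.047 |
| 6/20 vs 0/20 | 11.9–54.3% and 0–16.8% (overlap) | 0.020 |

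For 9/20 against 2/20 the relative risk is 4.5, exact interval about 1.2 to 38. With no events on placebo, the two intervals do not separate until 8/20 on dupilumab. Over all splits of 20 against 20 with more events in one given arm, 107 have Fisher p ≤ 0.05. In 35 of them (35/107 = 33%) the separate intervals still overlap.

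**Choice of interval for the risk difference.** When an arm has no events, the relative risk has no finite point estimate, whereas the risk difference is always defined. Its exact unconditional interval depends on how outcomes are ordered. One-sided p-values for no difference, to be compared with 0.025:

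| Events | Raw-difference ordering | Score ordering |
|---|---|---|
| 5/20 vs 0/20 | 0.077 | 0.008 |
| 6/20 vs 0/20 | 0.040 | 0.003 |

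The 95% interval includes zero in both cases under the raw ordering and excludes it in both under the score ordering. The plan therefore has to name the method.

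**The case against.** The protocol sentence is itself defective, so the SAP wording may be a repair: a percentage with an interval is something that can exist for each group. That is plausible, but a repair that removes the only between-arm estimate is still a change, and the SAP says there is no inconsistency.

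Descriptive safety reporting is normal in a 40-participant phase 2 trial. Relative risk intervals such as 1.3 to 213 say little, and with many categories a single unadjusted p-value near 0.05 proves nothing. All of this stands. It is why the contrast should be descriptive, and why Fisher p-values serve here only to illustrate.

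A reader might go further and infer four things that the documents do not support:
- That the SAP display hides imbalances. It does not: counts and percentages are given for both arms, so 8/20 against 1/20 is plain to see.
- That the SAP imposes a stricter test. It states no rule for judging safety by overlap of intervals.
- That nothing was set up to check safety. The protocol has grading tables, stopping rules, monthly monitor reports and safety board review. These are monitoring, not between-arm estimates, but they exist.
- That this is the only controlled safety evidence for dupilumab in eosinophilic gastritis. The documents do not say so; they support this only for the present trial.

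The weight of safety in the objectives should not be overstated either. The SAP Introduction says "The primary objective of this study is to assess the efficacy and safety of Dupilumab in the treatment of Eosinophilic Gastritis", but the formal primary objective in both documents concerns efficacy only, and the SAP's safety objectives ask for incidence, occurrence and severity, which the display does provide.

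**Conclusion.** The point holds as an undeclared loss of a pre-specified contrast. The SAP plans no between-arm safety estimate for the double-blind phase where the protocol planned a relative risk with an exact interval, and the SAP governs. No efficacy result, error rate or power figure is affected.

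The practical size is what separate intervals leave unsaid. At 20 per arm, about a third of the splits that reach Fisher p ≤ 0.05 still show overlapping per-arm intervals. That share counts possible splits; it is not a probability that such a result will occur. The conclusion rests on reading the protocol's relative risk as drug versus placebo, on arms of 20, and on assumed event counts. The textual discrepancy itself rests on none of the assumed counts. This should be corrected, and the correction is small.

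**What to change.** In the SAP section Safety outcomes, keep the per-arm display and add, for each adverse event and serious adverse event category in the double-blind phase:
- the risk difference, dupilumab minus placebo, with a score-based exact unconditional 95% interval, naming the score ordering explicitly; and
- the protocol's relative risk with an exact 95% interval where both arms have events.

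State that these are descriptive and carry no multiplicity claim. In Statistical Analysis Changes From the Protocol, list whatever then still differs from protocol 13.5.5, such as the added risk difference and the restriction of the relative risk to categories with events in both arms. If the sponsor prefers per-arm reporting only, the minimum is to declare and justify that in the same section.

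The cost is two more columns in the adverse event tables, with intervals that will visibly be wide. No new data are needed.

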### **Statistical Analysis Changes From the Protocol**

Changed the analysis population for the key primary and secondary efficacy outcomes to the complete case ITT. The rationale was that a single participant in the placebo arm dropped out before the end of the double blind. The initial SAP stated that multiple imputation would be used if missing data occurred. However, multiple imputation considers a multitude of plausible values and accounts for this uncertainty in the modelling. While it is a statistically robust approach, graphing the observed data points would exclude the missing data thus providing a mismatch between the graphical data and the statistical models used. Further, there was striking agreement between the results using the imputed and complete case datasets.

### **Conventions**

The precision of original measurements will be maintained in summaries, when possible. Means, medians and standard deviations will be presented with an increased level of precision; means and medians will be

presented to one more decimal place than the raw data, and the standard deviations will be presented to two more decimal places than the raw data.

Summaries of continuous variables that have some values recorded using approximate values (e.g., lab values < 0.001 or >200) will use imputed values. The approximate values will be imputed using the closest exact value for that measurement. For tables where rounding is required, rounding will be done to the nearest round-off unit. For example, if the round-off unit is the ones place (i.e., integers), values  $\geq$  XX.5 will be rounded up to XX+1 while values < XX.5 will be rounded down to XX.

Percentages will be based on available data and denominators will generally exclude missing values. For frequency counts of categorical variables, categories whose counts are zero will be displayed for the sake of completeness. For example, if none of the patients discontinue due to “lost to follow-up,” this reason will be included in the table with a count of 0. Categories with zero counts will not have zero percentages displayed.

## Standard Calculations

### EoG-EREFS

Will be calculated by location, by feature and as a total score. For fundus, body and antrum, the score will be the sum of the six features from each of the locations. For granularity, erosions, nodularity, erythema, friability and folds, the feature scores will be the sum of the feature of the three locations. The total score will be the sum of the six features of all three locations.

### EoE-EREFS

Will be calculated by location, by features and as a total score. For proximal and distal location, the score will be the sum of all five features from each of the locations. For edema, rings, exudates, furrows, and stricture, the feature score will be the sum of the proximal and distal scores of the feature. The total score will be the sum of all features from proximal and distal locations.

### EoD-EREFS

Will be calculated for duodenal bulb and duodenal, by features and as a total score. The score by location will be the sum of the seven features for the location, respectively. The feature score will be the sum of the feature from the two locations. The total score will be the sum of all features from both locations.

### EoG-SQ

**Total Symptom Score (TSS):** TSS will be based on patient-reported severity scores of stomach pain, stomach cramping, nausea, bloating, early satiety, and loss of appetite, with each reported on a 0-10 scale. These individual scores are summed on each day, with maximum daily score of 60. The post-baseline TSS is then calculated by averaging daily sum scores over all days with eDiary data in a 7-day period. At least 4 of 7days must be entered in the EG-SQ eDiary to derive the post-baseline TSS. The baseline TSS will be calculated from the 14 days prior to V1 (week 0). At least 8 of 14 days must be entered in the EG-SQ eDiary to derive the baseline TSS.

**Individual Symptom Scores (9 in total):** For each individual score, the post-baseline value is calculated by averaging daily scores with eDiary data in a 7-day period. At least 4 of 7days must be entered in the EG-SQ eDiary to derive the post-baseline score. The baseline value will be calculated from the 14 days prior to V1 (week 0). At least 8 of 14 days must be entered in the EG-SQ eDiary to derive the baseline.

When multiple records are available for a patient on the same day, the last record will be used for analysis. The analysis visit window for symptom diary data is outline below:

|          | Analysis Visit Window |
|----------|-----------------------|
| Baseline | Day -14 to Day -1     |
| Week 1   | Day 1 to Day 7        |
| Week 2   | Day 8 to Day 14       |

|         |   |
|---------|---|
| Week 3  | Day 15 to Day 21                            |
| Week 4  | Day 22 to Day 28                            |
| Week 5  | Day 29 to Day 35                            |
| Week 6  | Day 36 to Day 42                            |
| Week 7  | Day 43 to Day 49                            |
| Week 8  | Day 50 to Day 56                            |
| Week 9  | Day 57 to Day 63                            |
| Week 10 | Day 64 to Day 70                            |
| Week 11 | Day 71 to Day 77                            |
| Week 12 | Day 78 to Day 84                            |
| Visit 5 | Day -7 to Day -1 since end of double blind. |

**Note:**

- Diary study day = Diary date – 1st injection date in the study + 1 if diary date  $\geq$  1st injection date of study.
- Diary study day = Diary date – 1st injection date in the study if diary date  $<$  1st injection date of study.
- Day 1 is the day of the first study drug injection, and Day -1 is the day before. There is no Day 0.
- The first dose of OLE is administered at Week 12, and any diary data taken after the first dose of OLE will be excluded from analysis.

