3.5. Exploratory Endpoints/Outcomes for the OLE Population

There will be two key time points evaluated for the OLE. First, we will examine the overall change across the study (baseline to OLE/EOT (Week 24)). Second, we will examine change during the open label phase (DBP/EOT (Week 12) to OLE/EOT (Week 24)). These time points apply to all of the endpoints listed below.

- **Key Endpoint/Outcome:** Relative change of the peak eosinophil counts in the 5 most eosinophil dense HPFs in the gastric antrum and/or body

Additional Endpoints

- Absolute change in the mean of the peak eosinophil counts in the 5 most eosinophil dense HPFs in the gastric antrum and/or body
- Absolute change in the patient global impression of severity (PGI-S) score
- Patient global impression of change (PGI-C) score
- Proportion of participants achieving threshold response < 30 eos/hpf in all of the 5 hpfs identified
- Absolute change in endoscopic score as measured by Eosinophilic Gastritis Endoscopy Assessment.
- Absolute change in the total and each individual EG-SQ eDiary symptom score
- Absolute change in proportion of days with each individual symptom, multiple symptoms, and any (1 or more) symptom as measured by EG-SQ eDiary
- Absolute change in participant reported outcomes as measured by additional PROs including the Severity of Dyspepsia Assessment as well as QOL (SF-12, PROMIS 29 and PROMIS 25) scores. We will also utilize clinician global impression of severity and clinician global impression of change.
- Induction of disease remission defined by the percentage of participants who achieve histological remission in the stomach as defined by peak eosinophil counts less than 30/hpf in 1, 2, 3 and 4 of the 5 hpfs identified for the primary endpoint.
- Absolute change in histologic score as measured by the EG Biopsy Evaluation Form. For those participants with esophageal involvement or duodenal involvement, we will assess changes in histology using the EoE-HSS and ED Biopsy Evaluation Form respectively.
- Absolute and relative change in blood biomarkers (primarily cytokine levels) and tissue biomarkers as well as gastric transcripts
- Absolute and relative change in blood eosinophil count, hemoglobin, hematocrit, protein levels, IgE, iron storage panel (iron, ferritin, total iron-binding capacity)
- The association of blood and tissue biomarkers and transcripts with drug responsiveness.

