8.1.6. Schedule of Activities – Table A

Due to the public health emergency related to COVID-19, temporary alternative mechanisms to complete study procedures and drug administration may be required. All temporary mechanisms are described in section 8.4. If such mechanisms are utilized, they will be documented as related to COVID-19 and will only remain in effect during the public health emergency. Examples of such mechanisms include any of the following: phone contact, virtual visits, pick-up of study drug for home administration, use of local clinic or laboratory locations, and at-home pregnancy testing.

Schedule of Activities – Table A

Study Procedures	Screening	Double-blind Treatment							Open-label Extension										V8*	F/U**	
Visit ID	SC	V1	V2	V3	V4		EOT/ V5*		V6	T1		T2		T3							
Week (W)	W-8 to 0	0	2	4	6	8	10	12/0	2	4	6	8	10	12	14	16	18	20	22	24	36
Window (days [d])	---	---	±3d	±3d	±2d	±3d	±2d	±3d	±3d	±2d	±3d	±2d	±2d	±3d	±2d	±3d	±2d	±3d	±2d	±3d	±3d
Screening/Baseline																					
Informed Consent	x																				
Inclusion/Exclusion	x	x						x ¹													
Demographics, Med. History	x																				
Asthma Control Test (ACT)	x																				
Randomization		x ⁴																			
Treatment																					
Training for self-injection	x	x	x																		
Administer study drug ³	x	x	x	x ³	x	x ³	x ¹	x	x ³	x ³	x ³	x ³	x	x ³							
Monitor 30 min post injection (including post dose vital signs)	x	x	x				x	x													
Dispense Take Home Drug			x	x				x		x				x							
Concomitant Medications	x	x	x	x	x	x	x	x	x	x	x	x	x	x	x	x	x	x	x	x	
Diet Assessment	x	x	x	x	x	x	x	x	x	x	x	x	x	x	x	x	x	x	x	x	
Efficacy																					
EGD with biopsies (histology, RNA, protein)	x							x												x	
Histologic features (HSS EG, EoE, ED form)	x							x												x	
Endoscopy assessments (EoE-EREFs, EG-REFs, ED-EREFs)	x						x													x	
EG-SQ (Electronic Diary)	Daily from Screening to End of Study																				à
SODA§	x	x	x	x	x	x	x	x	x	x	x	x	x	x	x	x	x	x	x	x	
PROMIS 29‡	x							x												x	
PROMIS 25†	x							x												x	
EG-QOL‡	x							x												x	
SF12 Healthy Surveydo‡	x							x												x	
Patient global impression of severity (PGI-S)	x				x		x	x	x	x	x	x	x	x	x	x	x	x	x	x	

Schedule of Activities – Table A

Study Procedures	Screening	Double-blind Treatment							Open-label Extension										V8*	F/U**	
Visit ID	SC	V1	V2	V3	V4		TOT/ V5*		V6	T1		T2		TOT		T3					

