### ***Exploratory Objectives for the OLE Population***

Key Objective:

To assess the efficacy of repeat SC doses of dupilumab to reduce eosinophilic inflammation in the gastrointestinal tract of participants with EoG with or without esophageal and/or duodenal eosinophilia.

- To assess the efficacy of dupilumab as measured by:
  - Patient global impression of severity (PGI-S)
  - Patient global impression of change (PGI-C)
  - Proportion of participants achieving threshold response < 30 eos/hpf in 5 hpfs
  - Eosinophilic Gastritis Endoscopy Assessment (EoG-EREFS)
  - Eosinophilic Gastritis Symptom Questionnaire (EoG-SQ)
  - Comprehensive assessment of histologic features (EoG HSS)
- To assess the efficacy of dupilumab as measured by:
  - Severity of Dyspepsia Assessment (SODA)
  - Clinician global impression of severity (CGI-S)
  - Clinician global impression of change (CGI-C)
  - Quality of Life Questionnaire (SF12, PROMIS 29, PROMIS 25)
  - EoE Endoscopic Reference Score (EREFs) (participants with esophageal involvement)
  - Blood and tissue biomarkers and gastric transcripts
  - Peripheral eosinophil counts, hemoglobin & hematocrit, total protein and albumin, total IgE, iron storage panel (iron, ferritin, total iron-binding capacity)
  - Eosinophilic Duodenitis- Endoscopic Reference Score (EoD-EREFs)

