#### *Open Label Extension*

Two time points will be evaluated for the OLE: baseline to OLE/EOT and DBP/EOT to OLE/EOT for the endpoints listed below:

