#### Key Endpoint/Outcome

Relative change of the mean of the peak eosinophil counts in the 5 most eosinophil dense HPFs in the gastric antrum and/or body.

- 1) Absolute change in the mean of the peak eosinophil counts in the 5 most eosinophil dense HPFs in the gastric antrum and/or body
- 2) Absolute change in PGI-S score
- 3) PGI-C score
- 4) Proportion achieving threshold response < 30 eos/hpf in all of the 5 hpfs identified

- 5) Absolute change in endoscopic score measured by EoG-EREFS.
- 6) Absolute change in the total and each individual EoG-SQ eDiary symptom score
- 7) Absolute change in proportion of days with each individual symptom, multiple symptoms, and any (1 or more) symptom as measured by EoG-SQ eDiary
- 8) Absolute change in SODA, SF-12, PROMIS 29, PROMIS 25, and CGI-S scores.
- 9) CGI-C score
- 10) Induction of disease remission (percentage who achieve histological remission in the stomach as defined by peak eosinophil counts less than 30/hpf in 1, 2, 3 and 4 of the 5 hpfs identified for the primary endpoint).
- 11) Absolute change in EoG histology score (EoG HSS). For participants with esophageal involvement and/or duodenal eosinophilia involvement, absolute change in EoE HSS and EoD HSS, respectively.
- 12) Absolute and relative change in blood biomarkers, tissue biomarkers, and gastric transcripts
- 13) Absolute and relative change in blood eosinophil count, hemoglobin, hematocrit, total protein levels, albumin, IgE, iron storage panel (iron, ferritin, total iron-binding capacity)
- 14) The association of blood and tissue biomarkers and transcripts with drug responsiveness.
- 15) Absolute changes in esophageal and duodenal peak eosinophil levels.
- 16) Absolute changes in EoE-EREFS and EoD-EREFS in participants with esophageal and/or duodenal involvement, respectively.

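### As worded, the SAP's diary note removes the entries that its own exploratory open-label EoG-SQ endpoints need

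*SAP*

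**What the plan says.** **The exclusion.** In the SAP, Standard Calculations, EoG-SQ, the diary window table has a Baseline row, rows for Weeks 1 to 12 (the last is Days 78 to 84), and a Visit 5 row covering the seven days before the end of the double-blind phase. No OLE row follows. The note below the table places the first OLE dose at Week 12 and adds that "any diary data taken after the first dose of OLE will be excluded from analysis".

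**The planned endpoints.** EoG-SQ is among the SAP's exploratory objectives for the OLE population. Under Open Label Extension the SAP states: "Two time points will be evaluated for the OLE: baseline to OLE/EOT and DBP/EOT to OLE/EOT". The list that follows includes, as items 6 and 7, "Absolute change in the total and each individual EoG-SQ eDiary symptom score" and "Absolute change in proportion of days with each individual symptom, multiple symptoms, and any (1 or more) symptom as measured by EoG-SQ eDiary". Under Efficacy Analyses, Exploratory Endpoints, "Changes of the OLE endpoints will be tested against 0 using paired t tests or signed rank tests".

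**The protocol.** Section 3.5 plans the same endpoint: "Absolute change in the total and each individual EG-SQ eDiary symptom score". Table A in section 8.1.6 schedules the diary "Daily from Screening to End of Study". Section 8.1.2 takes the end-of-open-label score from OLE weeks 22 to 24.

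**The concern.** Both planned OLE changes, from baseline and from the end of the double-blind phase, need a diary value at the end of the OLE. Every entry that could supply one is recorded after the first OLE dose, and the note excludes it. The note's wording covers diary data in general, and the table above it is likewise introduced as the window table for the symptom diary, not for the double-blind phase alone.

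A programmer who follows the note produces no OLE EoG-SQ results. One who ignores it must choose where the end-of-OLE window sits, because the SAP's table does not place one. At stake is whether the exploratory open-label symptom summaries exist and are derived by a rule written down beforehand. This matters more because the SAP's Introduction labels any analysis it does not define prospectively as post hoc.

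**Working it through.** The plan gives no figure to reproduce. The check is whether any diary day that could supply an OLE/EOT value survives the note.

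**Inputs**

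- Day 1 is the first injection and there is no Day 0 (SAP, EoG-SQ note).
- The first OLE dose is given at Week 12 (SAP, EoG-SQ note). On schedule this is Day 12 × 7 + 1 = 85.
- Visit 8 falls at OLE week 24, within 3 days either way, counted from the first open-label dose (Protocol 8.4.2).
- The SAP scores post-baseline symptom values over 7 days and requires at least 4 entries (SAP, EoG-SQ).
- The protocol's end-of-OLE window is weeks 22 to 24 (Protocol 8.1.2), taken here as OLE weeks.

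**Nominal days**

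- Visit 8: 85 + 24 × 7 = 85 + 168 = Day 253.
- Seven days before Visit 8: 253 − 7 = 246 to 253 − 1 = 252, so Days 246 to 252.
- OLE weeks 22 to 24: 85 + 154 = 239 to 85 + 167 = 252, so Days 239 to 252 (14 days).

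**Days that survive the note**

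- Days on or before Day 85 within Days 246 to 252: 0 of 7, against a minimum of 4.
- Days on or before Day 85 within Days 239 to 252: 0 of 14.
- OLE days (Days 85 to 252, 168 in all) that fall in any Week 1 to 12 row: 0, because those rows end at Day 84. The Visit 5 row looks backward and adds none.

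**Sensitivity to the schedule.** Let the first OLE dose be on day D and Visit 8 on D + 168 + s. The 7-day window then starts on D + 161 + s. With s between −3 and +3, the earliest possible start is D + 158, well after D. Reading the protocol's weeks 22 to 24 as study weeks gives Days 155 to 168, which also follow Day 85. The count of zero does not depend on these choices.

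**Consequence for the two endpoints.** For item 6, no score meets the 4-of-7 rule. For item 7, the proportion of symptom days has no days in its denominator. Neither the change from baseline nor the change from DBP/EOT has an end value.

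**What the note is for.** Visit 5 may fall 3 days early, on Day 82. If the first OLE dose is given that day, Days 83 and 84 of the Week 12 row come after it. Keeping such days out of a double-blind score is a sound purpose, and the note's position under a double-blind table fits it. That purpose does not require excluding Days 246 to 252.

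**The case against.** The strongest reply is that the intended meaning is obvious. The note sits directly under a table running from Baseline to Visit 5. The SAP keeps EoG-SQ as an OLE objective and endpoint. Its section on changes from the protocol does not list any removal of these endpoints, and its Introduction describes its analyses as consistent with the protocol. On this view only a short scoping phrase is missing. The SAP also requires independent program validation and senior statistical review, so two named endpoints with every value missing would probably be noticed.

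Most of this stands. The narrow reading is almost certainly the intended one, and a silent loss of the endpoints is unlikely. But validation checks programs against the plan, and here the plan states two incompatible things. Narrowing the note also still leaves the OLE window without a position in the SAP's table.

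Two stronger readings are tempting, and the documents do not support them:

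- A reader might infer that the SAP's precedence over the protocol makes the exclusion prevail and cancels the OLE diary endpoints. That clause settles differences between protocol and SAP. Here one part of the SAP conflicts with another, and the clause does not rank them.
- A reader might infer that the SAP has no rule at all for scoring the OLE diary. The 7-day length and the 4-of-7 minimum for scores are already written as general post-baseline rules. What the table lacks is the OLE anchor.

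**Conclusion.** The point holds as a conflict within the SAP. Applied as written, the note leaves 0 of 7 usable days before Visit 8 and 0 of 14 in the protocol's window, so the exploratory OLE EoG-SQ changes cannot be computed. This is more than missing detail, because a stated rule gives the wrong result for endpoints that the same document plans.

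The reach is small. Only uncontrolled exploratory OLE summaries are affected. The primary endpoint, the testing hierarchy and the double-blind treatment comparison are not. Nothing suggests that the sponsor meant to drop the OLE symptom endpoints.

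The day numbers assume an on-schedule Visit 5 and Visit 8, with the first OLE dose on the day of Visit 5. The zero counts hold across the permitted visit windows. One limit remains: the SAP's last heading, Study Design/Visits, has no content in the text available, so an OLE diary window stated there cannot be ruled out. The unscoped exclusion would still conflict with it.

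**What to change.** 1. Limit the exclusion in the EoG-SQ note to the double-blind windows and endpoints.
2. Add one OLE/EOT row to the diary window table that mirrors the Visit 5 row: Day −7 to Day −1 before Visit 8, with at least 4 of 7 days under the existing post-baseline rule. Both ends of the DBP/EOT-to-OLE/EOT change then use the same window. State that this differs from the protocol's OLE weeks 22 to 24.
3. Date the edit as a clarification. The SAP's section on changes from the protocol shows that imputed and complete-case results had already been compared. Anchoring to Visit 8 is a choice, since Protocol 8.4.2 counts OLE visit windows from the first open-label dose. It does follow the Visit 5 precedent, and the record should say so.

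The cost is one phrase, one table row and minor programming. No new data are needed.
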